## **4.2 Screening Exclusion Criteria**

- 4.2.1** Clinically suspicious mass/lesions.
- 4.2.2** Breast cancer in the past 5 years.
- 4.2.3** Patients with any history of venous thromboembolic disease, regardless of timeframe (history of varicose veins and superficial phlebitis is allowed).
- 4.2.4** Current pregnancy or lactation.
- 4.2.5** History of other prior breast cancer-specific therapy within the previous 2 years (chemotherapy, anti-HER2 agents, endocrine agents, everolimus, CDK4-6 inhibitors).
- 4.2.6** Cytotoxic chemotherapy for any indication in last 2 years.
- 4.2.7** Prior use of SERMS or AIs including tamoxifen, raloxifene, anastrozole, letrozole, or exemestane for prevention or therapy within the past 5 years. UNLESS
  - a) Use was less than 6 months duration in the past 5 years and not used in the 1 year prior to enrollment, OR
  - b) Use was no greater than 2 months duration in the past 1 year and not used in the 6 months prior to enrollment.
- 4.2.8** Exogenous sex steroid, including oral contraceptive pill use within 1 month

prior to Pretreatment breast biopsy (). Use of vaginally administered estrogens and hormone coated IUD such as Mirena is permitted

**4.2.9** History of any prior ipsilateral breast radiotherapy. Previous unilateral radiation of the contralateral side is allowed.

**4.2.10** Skin lesions on the breast that disrupt the stratum corneum (e.g., eczema, ulceration).

**4.2.11** History of endometrial neoplasia.

**4.2.12** Current smoker. Cessation for at least 6 weeks.

**4.2.13** Current users of potent inhibitors of tamoxifen metabolism. The potent inhibitors of tamoxifen metabolism are: bupropion, cinacalcet, fluoxetine, paroxetine, quinidine.

**4.2.14** Participants may not be receiving any other investigational agents within 90 days of enrollment or during this study.

**4.2.15** History of allergic reactions to tamoxifen.

**4.2.16** Uncontrolled intercurrent illness that in the judgement of the treating physician would make them unsuitable for study participation.

**4.2.17** Current use of anticoagulation medications.

**4.2.18** Patients who are breastfeeding.

**4.2.19** Participant will be excluded with any one or more of the following results within 30 days of randomization:

- Hemoglobin < 10 g/dL
- Leukocytes < 3,000/microliter
- Platelets < 100,000/microliter
- Total bilirubin > 1.5 x institutional upper limit of normal (ULN)
- AST (SGOT) > 1.5 x ULN
- ALT (SGPT) > 1.5 x ULN
- Alkaline phosphatase, S > 1.5 x ULN
- Albumin, S > 1.5 x ULN
- Protein, total, S > 1.5 x ULN
- Creatinine > 1.5 x ULN
- Antithrombin III < 80% of normal
- Fibrinogen > 1000 mg/dL

**4.2.20** Patients who are taking any medications, herbal products, or OTC products that are moderate or strong CYP2D6 inhibitors or CYP3A inducers. Patients should also refrain from starting any drug or product with these properties during the study. This is to avoid any potential interactions with tamoxifen or 4-OHT. (Please see Appendix G.)

**4.2.21** Clinically significant arrhythmia requiring ongoing medication for control / treatment, especially those with high risk of QT prolonging effects (Appendix H).

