### **Expansion of Eligibility Criteria April 2023**

In order to expand the pool of eligible patients for the trial we will include patients without atypical hyperplasia or LCIS but who are at increased risk for breast cancer based on risk model calculations that are concordant with current consensus guidelines. For women at increased risk based on Gail / Breast Cancer Risk Assessment Tool 5-year risk 3%, or International Breast Intervention Study 10-year risk 5%, breast cancer prevention therapy is RECOMMENDED (Visvanathan Journal of Clinical Oncology 2019;37(33):3152-65, NCCN Guidelines v1.2023), and therefore these women are appropriate for inclusion in this trial of short-term oral versus 4OHT topical tamoxifen. In addition, we will also allow short periods of prior use of risk-reducing medications with corresponding periods without use prior to study participation (see Exclusion criteria).

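### As written, exclusion 4.2.7(b) limits SERM/AI use only in the past year, so it admits women with long preventive use, against the stated aim of allowing only short prior use

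*Combined protocol and SAP*

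**What the plan says.** Section 4.2.7 sets a five-year look-back: "Prior use of SERMS or AIs including tamoxifen, raloxifene, anastrozole, letrozole, or exemestane for prevention or therapy within the past 5 years". Two exceptions follow, joined by OR.

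- Exception (a): "Use was less than 6 months duration in the past 5 years and not used in the 1 year prior to enrollment".
- Exception (b): "Use was no greater than 2 months duration in the past 1 year and not used in the 6 months prior to enrollment".

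The Background section headed Expansion of Eligibility Criteria April 2023 gives the purpose: "we will also allow short periods of prior use of risk-reducing medications with corresponding periods without use prior to study participation".

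Two neighbouring criteria bear on the same women. Section 4.2.2 excludes breast cancer in the past five years. Section 4.2.5 excludes "History of other prior breast cancer-specific therapy within the previous 2 years", and its list includes endocrine agents.

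**The concern.** Exception (a) limits duration over five years. Exception (b) limits it over one year and is silent on the other four. Because either exception is enough, a woman with years of preventive tamoxifen can enter through (b) once she has been off it long enough. That is not a short period of prior use.

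Eligibility is confirmed by study coordinators from medical records at three sites (4.5 and 9.3.1), so the literal wording is what would be applied. Nothing later in the plan separates these women out. Prior SERM/AI use is not a stratification factor (6.0). The sensitivity analyses in 11.0 drop only non-compliant patients or the 4 mg/day gel group.

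The primary endpoint is percent change in Ki67 from baseline, and the Background says tamoxifen lowers both Ki67 in normal lobules and mammographic density. If some of that effect outlasts treatment, baseline values in prior long-term users could be altered and their change on study smaller. Section 5.0, note 8, also lets a diagnostic biopsy up to six months before enrollment serve as baseline tissue. A woman who stopped 10 months before enrollment could therefore have baseline tissue taken 10 − 6 = 4 months after her last dose.

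**Working it through.** **The rule.** The plan gives no figure for this rule, so the check is of its logic. Take every single continuous course of use, in whole months, within the 60 months before enrollment. A course starts s months ago and ends e months ago, with s > e, which gives 60 × 61 / 2 = 1,830 courses. These are possible histories, not proportions of women.

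*Meeting (a):* e ≥ 12 and length 1 to 5 months.
- e = 12 to 55 gives 44 × 5 = 220.
- e = 56 to 59 gives 4 + 3 + 2 + 1 = 10.
- Total 230.

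*Meeting (b) as written:* e ≥ 6 and at most 2 months of use inside the past 12.
- For e ≥ 10, any start qualifies: 50 + 49 + … + 1 = 1,275.
- For e = 6 to 9, only lengths of 1 or 2 months qualify: 4 × 2 = 8.
- Total 1,283.

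*Meeting (a) but not (b):* none. No use in the past year means 0 months (at most 2) and none in the last 6. About 300,000 random histories of one to three courses gave the same answer: 89,810 met (a), and all of them met (b).

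*Long use admitted by (b):* 45 × 46 / 2 = 1,035 courses have at least 6 months of use, and 39 × 40 / 2 = 780 have at least 12. The longest runs from month 60 to month 10, which is 50 months. A 48-month course ending 12 months ago fails (a) and passes (b).

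**Narrower readings of (b).**

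| Reading | Courses meeting (b) | With ≥12 months of use | Longest use | Is (a) redundant? |
|---|---|---|---|---|
| As written | 1,283 | 780 | 50 months | yes |
| Some use in the past year is required | 107 | 77 | 50 months | no |
| All use in 5 years is at most 2 months and reaches into the past year | 12 | 0 | 2 months | no |

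Only the last reading closes the gap, and the text does not say it.

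**Possible effect on the primary comparison.** Inputs from 11.0, Sample size/power: SD 30, margin 20 points, 36 per active arm, tamoxifen mean change −50. I use a normal approximation and take non-inferiority to mean that the two-sided 95% interval for gel minus tamoxifen lies below 20.

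*The plan's own power.* SE = √(2 × 900 / 36) = 7.07. Power with equal agents = Φ(20/7.07 − 1.96) = Φ(0.87) = 81%, in line with the stated 80%.

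*With an inert fraction.* Assume that a fraction f of both arms has mean change 0 and SD 30. An arm whose other women have mean μ then has mean (1 − f)μ and variance 900 + f(1 − f)μ². The chance of declaring non-inferiority is Φ((20 − true mean difference)/SE − 1.96).

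Worked case, f = 0.10:
- Means −50 and −30 in the other women: the difference is 18, the variances are 1,125 and 981, and SE = √(2,106/36) = 7.65. Φ(2/7.65 − 1.96) = Φ(−1.70) = 4.5%.
- Both means −50: SE = √(2,250/36) = 7.91. Φ(20/7.91 − 1.96) = Φ(0.57) = 72%.

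| f (assumed) | False non-inferiority (gel 20 points worse in the other women) | Power (agents equal) |
|---|---|---|
| 0 | 2.5% | 81% |
| 5% | 3.4% | 76% |
| 10% | 4.5% | 72% |
| 15% | 5.7% | 68% |

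**The case against.** The authors probably intended two tiers: longer use with a longer gap, shorter use with a shorter gap. The word corresponding in the expansion text points that way, and under that reading the gap disappears. This is a fair account of intent, but the clause does not say it, and sites will apply the clause.

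Other criteria also narrow the gap. Sections 4.2.2 and 4.2.5 remove women with recent breast cancer and those given endocrine agents as cancer therapy in the last two years. That stands, so the long-use example has to be preventive use, which 4.2.5 does not clearly reach.

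A reader might infer that (a) is void on any reading. It is not. Redundancy requires that zero use in the past year count as meeting (b). If some use in that year is required, (a) has a role again, although 50 months ending 10 months ago still passes.

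A reader might also infer that the rule biases the trial towards non-inferiority. The documents do not support that as a finding. They give no count of such women and no evidence that Ki67 is still altered months after stopping. A single long course must have ended at least 10 months before enrollment to qualify, and the Background names toxicity as a barrier to uptake and long-term compliance, so such women may be few. The same assumed mixture that raises the false-positive rate also makes a correct non-inferiority conclusion less likely.

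**Conclusion.** The point holds as a defect of wording with a real consequence for who may enter. Read literally, 4.2.7(b) admits up to 50 months of preventive SERM/AI use within the look-back, which contradicts the stated aim of short prior use. The six-month limit in (a) excludes nobody if zero use in the past year satisfies (b).

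The effect on the primary comparison is unknown. The error and power figures above illustrate an assumed 5% to 15% of women with no Ki67 response in both active arms, and neither the fraction nor the absence of response comes from the documents. At 5% both effects are small. The planned sample size and stated power do not depend on this rule and do not change.

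**What to change.** Reconcile 4.2.7 with the April 2023 expansion text. Make the duration limit in (b) apply to total use over the same five-year look-back as the main criterion. Word (a) and (b) as two distinct tiers, the longer permitted use with the longer use-free period and the shorter with the shorter. The sponsor should confirm the limits.

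Copying the six-month limit from (a) into (b) would not be enough. It reduces the longest admitted use from 50 to 5 whole months and the qualifying courses from 1,283 to 248, but every woman meeting (a) would still meet (b). It would also admit, for example, 5 months of use ending 10 months ago, without the one-year interval that (a) requires.

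The cost is one reworded clause in the eligibility list. A few women with long past use become ineligible, as the expansion text appears to intend.

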#### **4.3 Enrollment – Inclusion Criteria**

**4.3.1** Negative pregnancy (serum or urine) test if of childbearing potential and/or FSH to verify menopausal status.

#### **4.4 Enrollment – Exclusion Criteria**

**4.4.1** Identification of a clinically suspicious mass on examination

#### **4.5 Identification of Potential Participants**

Study coordinators will identify potential patients by reviewing breast clinic and breast surgeons' patient schedules for women diagnosed with ALH, ADH, LCIS or increased breast cancer risk as calculated by the breast clinic or other medical provider . Their

return appointment(s) schedule(s) will be reviewed for possible patient contact times. Patient charts will be reviewed to identify if they meet inclusion and exclusion criteria.

#### 4.6 Patient Consent

The patients who meet study eligibility will be approached by the study coordinator prior to, during or after their clinical appointment to discuss the purpose of the study and what involvement in the study would entail. The consent form will be reviewed. If the patient agrees to be part of the study, they will be asked to sign the consent. A copy of the signed consent will be provided to the patient.

#### 5.0 Test Schedule

Test & Procedures	Baseline	End of Treatment (at the end of 4 weeks of treatment) 
Pregnancy Test (serum or urine)	X 	
Follicle stimulating hormone (FSH)	X 	
Baseline labs [CBC and Liver Function testing (ALP, ALT, AST, ALB, TP, BILI), creatinine coagulation labs (fibrinogen, Antithrombin 3)]	X 	X 
Physical Examination	X 	X 
Two 10 ml amounts of blood (will be stored for future research)	X 	X 
Blood Draw (4-OHT bioavailability)		X 
Research Biopsy of Breast Tissue - same quadrant as diagnostic biopsy  [Ki67, NanoString, 4-OHT bioavailability (post-treatment only);] Pretreatment diagnostic biopsy is OPTIONAL if meets requirements	X 	X 
Digital Screening Mammogram	X 	X 
MBI (Mayo Clinic site only)	X 	X 
BCPT Symptom Survey	X 	X 
Symptom /safety/AE assessment	X 	X 

1. For women of childbearing potential only.
2. Research Funded (Note: clinical surgical consult will not be research funded.)
3. For women with unknown menopausal status
4. Physical exam could be done within 3 months before treatment starts.

5. Blood for storage two 10 ml blood draws using purple top EDTA tubes – protect from light exposure (i.e., wrap in tin foil, use light sensitive brown bags). **First EDTA tube**- Aliquot (1) 4000uL blood pour for DNA extraction. Refrigerate, Centrifuge at lab standards. Process for three 1 ml aliquots of plasma into 3 cryovials 1 ml plasma each and 1ml WBC. Light Sensitive. Store in -80 freezer. **Second EDTA vial** is stored as whole blood.
6. Blood for 4-OHT bioavailability. 4 ml. green top heparin tube. Process for plasma. Protect from light exposure as light sensitive (i.e., wrap in tin foil, use light sensitive brown bags). Store in -80 freezer.
7. Baseline Pretreatment research tissue core biopsy information is located in Appendix F.
8. Pretreatment (baseline OPTIONAL) research tissue. This is optional if the subject has a pretreatment diagnostic breast biopsy that is 1) within 6 months of enrollment, 2) no exogenous sex steroids other than vaginal estrogen or hormone coated IUD within one month prior to the diagnostic biopsy, 3) has at least 4 normal TDLUs by pathologist review, and 4) if the FFPE tissue from the diagnostic biopsy will be available to the research study for primary (Ki67) and secondary tissue endpoints (RNA extraction). If Pretreatment research biopsy is performed, tissue will be collected by doing vacuum assist core biopsy, using a 9-11G needle. At Mayo Clinic, snap frozen tissues will be stored in BAP, and batch shipped to [name] lab in Jacksonville, FL; formalin fixed cores will be delivered to the Clinical Histology lab to create a single FFPE block if possible and a single H&E stain for each block. The H&E stained slide(s) will be delivered by the study coordinator to the breast pathologist, [name], or her designee, for core biopsy read within 21 days of biopsy. After the breast pathologist's review is complete, the FFPE blocks and H&E will be stored and batch shipped to [name] lab in Jacksonville, FL for Ki67 IHC, slide scanning at 40X, and Aperio quantitation. At Northwestern University and MD Anderson Cancer Center at Cooper, snap frozen cores will be stored at -80, and shipped to [name] lab in Jacksonville; formalin fixed cores will be put up as a single FFPE block if possible (see details section 6.8.3). (Note, there will not be 4OHT testing on pretreatment breast tissue samples.)
9. The post-treatment research breast tissue sample is MANDATORY and can be obtained by either needle core approach (if no surgical excision is done for clinical care) or can be obtained by the surgical team intraoperatively after excision of the lesion and negative margins are obtained diagnostically. If core biopsy approach is used for the post-treatment sample, follow guidelines in #8 above. If surgical excisional biopsy is performed for clinical care, the post-treatment samples will be obtained by the surgical team. Two 1 cm^2 pieces of tissue will be excised by the surgeon after negative margins have been obtained diagnostically. One of these two pieces of tissue should be cut in half and placed into two separate sterile tubes for snap freezing-- one piece will go for 4-OHT to [name] lab, and one for RNA extraction to [name] lab. The other 1 cm^2 piece of tissue will be put in formalin and processed in the Clinical Histology Lab for a single FFPE block and one single H&E stain. The H&E stain will be delivered by the study coordinator to the breast pathologist, [name], or her designee, for core biopsy read within 21 days of biopsy. After the breast pathologist's review is complete, the FFPE blocks and H&E will be stored and batch shipped to [name] lab in Jacksonville, FL for Ki67 IHC, slide scanning at 40X, and Aperio

quantitation.

10. Bilateral CC view (FFDM), 1 CC view of each breast.
11. MBI to be obtained at baseline. This will not be required if a current MBI was done within one month of starting treatment.

Tests to be scheduled as described above, with the last dose of study drug within 2 days (preferably within 24 hours) prior to the post-treatment biopsy and blood draw. All other tests (mammogram, MBI) should be scheduled PRIOR to the post-treatment breast biopsy, but no more than 3 days prior.

Participants will receive a total of \$350.00 to \$500.00 for completing the study. This will be paid as \$350 upon completion of study intervention and post treatment tests and biopsy, with an additional \$150 for subjects who undergo the pretreatment research biopsy (given at completion of pretreatment research biopsy). All participants will also receive a small gift of appreciation.

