## **6.7 Treatment Start**

After study randomization and all baseline evaluations are obtained, patients will begin treatment. Treatment must start within three months of baseline physical exam and labs, with Mammogram, MBI, and research core biopsy (if applicable) performed no longer than 7 days prior to starting treatment.

These studies should be coordinated with the date they can return for follow-up testing (or date of surgical excision if applicable).

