*Feasibility.* At Mayo Clinic in Rochester, MN, we see an average of 55 patients per year with ADH or ALH who would be eligible for this study. At Mayo Clinic, Drs. [name], [name], and [name] have successfully led accrual of over 500 women to prospective studies in the last six years, therefore successful accrual of women to this prospective study is feasible. At Northwestern University, there is a similar volume of women with diagnoses of ADH or ALH, and they have accrued ~400 women over five years to various studies requiring some form of intervention (either medication or biopsy). Accrual plan is for 42 subjects at Mayo Clinic, 42 at Northwestern University and 20 subjects at MD Anderson Cancer Center at Cooper. With an anticipated timeframe of 48 months to complete accrual, this averages to 1-2 patients per month per site. This study should be acceptable to patients as the duration of intervention is short and therefore short-term

toxicity is expected to be limited to only temporary vasomotor symptoms.

*Translational studies.* The primary endpoint will be change in Ki67 in background normal breast lobules (% cells positive by Aperio quantitation). Additional endpoints will include changes in volumetric density (% and dense volume) measured using VolparaTM both at baseline and after four weeks of treatment. In addition, promising genes from discovery work in Aim 2 will be evaluated using NanoString.

Changes in background parenchymal uptake (BPU) on MBI will also be employed as an exploratory endpoint. Blood samples and residual breast tissues collected pre/post Tam will be stored for future correlative studies.

*Endpoints.* The primary endpoint is change in Ki67 level pre/post treatment. The primary analysis for the primary endpoint will include all eligible patients who began study drug intervention and have available tissue measures of Ki67 levels at both timepoints (pre- and post-treatment).

A sensitivity analysis for the primary endpoint will also be performed. This sensitivity analysis will include eligible patients who have available tissue measures of Ki67 levels at both timepoints and were compliant with study treatment. Patients will be classified as non-compliant with the study treatment (and thus excluded from the sensitivity analysis) using criteria outlined above (patients who have less than 80% compliance with daily drug use or have missed more than 3 doses in the final 14 days).

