*Statistical analysis.* The primary hypothesis is that the reduction seen with 4-OHT gel will be *not inferior* to that seen with oral tamoxifen. We also hypothesize that oral tamoxifen and 4-OHT gel will each be superior to placebo with respect to the percent change in Ki67 in background normal lobules between baseline and four weeks. Analyses will assess if significant changes in Ki67 are observed after four weeks of treatment by paired t-tests/Wilcoxon signed rank tests, stratified by treatment group. We will assess the non-inferiority of 4-OHT gel compared to oral tamoxifen by estimating a 95% confidence interval for the mean *difference* in percent change between the two agents after four weeks of treatment; if the lower limit of the confidence interval is less than the non-inferiority margin (described below), we will conclude that 4-OHT gel is non-inferior to oral tamoxifen. As exploratory analyses, we will assess pairwise differences between samples on active treatment (oral tamoxifen or 4-OHT gel, separately and combined) vs. placebo using two-sample t-tests/Wilcoxon rank sum tests. Similarly, we will assess changes from baseline in the expression of the candidate genes identified in Aim 2 (absolute log2 fold-change > 2 and/or q-value < 0.05). Volumetric density changes from baseline within treatment group will be assessed continuously, and evaluated using paired t-tests on the log-transformed density or Wilcoxon signed-rank tests; pairwise differences between treatment groups will be assessed with two-sample t-tests/Wilcoxon rank sum tests. BPU on MBI is measured as a four category ordinal scale; we will compare pre-to-post changes within group using Wilcoxon signed rank tests and will compare the percent of subjects decreasing BPU category by one or more level between groups using chi-square tests. We will assess the correlation between changes in volumetric density and changes in BPU, using Spearman correlation. Symptoms from the BCPT survey are measured on a five-level ordinal scale. We will compare differences in pre- to post-treatment symptom severity changes across

treatment arms using Wilcoxon rank sum tests.

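### The Ki67 analyses ignore which kind of tissue each sample came from; adjusting for source could sharpen the primary comparison, and the within-arm tests should be read against placebo

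*Combined protocol and SAP*

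**What the plan says.** **Baseline tissue.** Section 5.0, footnote 8, on the pretreatment research biopsy: "This is optional if the subject has a pretreatment diagnostic breast biopsy that is 1) within 6 months of enrollment". Three further conditions apply: no exogenous sex steroids in the month before that biopsy (with exceptions), FFPE tissue available to the study, and that the biopsy "has at least 4 normal TDLUs by pathologist review". Women without such a biopsy have a fresh core; Section 6.7 requires the "research core biopsy (if applicable) performed no longer than 7 days prior to starting treatment".

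**Post-treatment tissue.** Footnote 9 makes this sample mandatory but allows it to be obtained "by either needle core approach (if no surgical excision is done for clinical care) or can be obtained by the surgical team". Section 7.3.2 describes the surgical option.

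**Analysis.** Section 11.0 takes all eligible women who began study drug and have Ki67 at both times. Within-arm change is tested "by paired t-tests/Wilcoxon signed rank tests, stratified by treatment group". Non-inferiority is judged by "estimating a 95% confidence interval for the mean" difference in percent change between gel and tamoxifen. No covariates are named. Comparisons with placebo are called exploratory. Section 6.0 stratifies randomisation by site, diagnosis and menopausal status, not by sample source. The two sensitivity analyses for the primary endpoint concern compliance and gel dose.

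**The concern.** Allowing either source is a sensible feasibility choice. But a woman's two samples may then differ in more than treatment. A diagnostic baseline can be months old and comes from the lesion site, whereas Appendix F targets the research core about 1 cm from it. Under Section 6.8.3 a diagnostic baseline is sent as unstained sections, while research cores are sent as FFPE blocks.

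If source shifts the measured percent change in Ki67, there are two consequences:

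- **Between arms.** Unmodelled source variation stays in the error term and widens the non-inferiority interval.
- **Within arm.** Randomisation does not protect a pre/post test. A shift towards lower readings passes for a drug effect, and the opposite shift hides one. This matters because, with the placebo contrasts exploratory, the paired tests are the main planned evidence that Ki67 fell at all. A finding that gel is no worse than tamoxifen means little unless tamoxifen worked.

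**Working it through.** **Inputs from Section 11.0.** SD of percent change 30 points, margin 20 points, 36 per active arm, 18 placebo, two-sided 95% interval (0.025 one-sided). True difference taken as 0. I read the decision rule in its usual sense: the interval must exclude a gel disadvantage of 20 points.

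**Assumed, because the documents give no figure.** One binary source factor; a proportion p of women on one source, with p = 0.5 unless stated; a shift d of 10, 20 or 30 points in mean percent change between sources.

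**1. The plan's own figure.** SE = 30 × √(2/36) = 7.07; noncentrality = 20/7.07 = 2.83 on 70 df. Noncentral-t power is 79.7% (80.7% by the normal approximation), against a stated figure above 80% and 80% in Table 1. The same method reproduces every entry of Table 1 (80/81/83/85% and 76/78/80/82%).

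**2. Between-arm precision.** An unmodelled source adds p(1−p)d² = 0.25d² to the variance. Two cases arise, because Section 11.0 does not say whether its SD of 30 already contains source variation.

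| d | A: SD = √(900 + 0.25d²) | A: unadjusted power | B: residual SD = √(900 − 0.25d²) | B: adjusted power |
|---|---|---|---|---|
| 0 | 30.0 | 79.7% | 30.0 | 79.7% |
| 10 | 30.4 | 78.6% | 29.6 | 80.8% |
| 20 | 31.6 | 75.4% | 28.3 | 84.1% |
| 30 | 33.5 | 70.4% | 26.0 | 89.6% |

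- In case A (30 excludes source), adjustment restores roughly 79–80%.
- In case B (30 includes source), unadjusted power stays at 79.7%, and adjustment adds to it.
- With p = 0.3, case A gives 78.7%, 76.0% and 71.8%.
- With two independent factors (baseline and post-treatment, p = 0.5 each), case A gives 77.5%, 71.3% and 62.5%.

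**3. Between-arm bias.** In simulation with the true difference at the margin and source ignored, one-sided type I error was 2.5–2.6% for d = 0, 20 and 30. Chance imbalance in source between arms has SD √(2 × 0.25/36) = 0.118. This moves the estimate by about 1.2, 2.4 or 3.5 points in either direction.

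**4. Within-arm tests with no drug effect.** Bias = p × d; noncentrality = bias/(SD/√n), using the case A SD. For n = 36 and d = 20: 10/(31.62/6) = 1.90.

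| d | Bias (points) | False positives, n = 36 | False positives, n = 18 |
|---|---|---|---|
| 10 | 5 | 16.0% | 10.1% |
| 20 | 10 | 45.4% | 24.5% |
| 30 | 15 | 74.2% | 43.3% |

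The nominal rate is 5%.

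**The case against.** The case for leaving the plan alone has real substance.

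- **Safeguards exist.** Ki67 is read in background normal lobules, not in the lesion. A diagnostic baseline must meet the TDLU and hormone conditions. Surgical tissue is taken after negative margins, the second sample comes from the same quadrant, and one laboratory does staining and quantitation. These steps may keep the source effect small. They limit it but do not adjust for it.
- **The effect is unknown.** A 30-point shift equals the whole assumed SD and is 60% of the expected 50-point tamoxifen effect; nothing in the documents supports it. An even split is also the worst case for added variance. At 10 points the half-width of the interval moves only from 14.1 to 14.3.
- **The placebo arm is a check.** It follows the same sampling rules, so a common artefact should appear there too. This stands, but the arm has only 18 women and the plan does not make its contrasts the basis for reading the within-arm results.
- **Diagnosis is a stratification factor** and may partly stand in for source, since women enrolled on risk-model criteria may have no recent biopsy. However, Section 11.0 does not adjust for the stratification factors either.

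A reader might infer that the non-inferiority comparison itself is biased. It is not: assignment is randomised and blinded, source balances on average, and the simulated error rate holds. A reader might also infer that power is certainly below plan. That follows only if the SD of 30 excludes source variation, which the documents leave open.

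**Conclusion.** The point holds as a cheap improvement, not as a flaw in the primary comparison. The plan mixes tissue sources at both times and has no analysis that takes account of it. For gel versus tamoxifen, what is at stake is precision: about 1, 4 or 9 percentage points of power for assumed shifts of 10, 20 or 30 points in case A, or a comparable or larger gain forgone in case B. For the within-arm tests, what is at stake is validity: under the same assumptions, false-positive rates of about 16%, 45% and 74% at 36 women, with placebo the only check.

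All of these sizes rest on assumed source effects and an even split. Covariates remove only a mean shift; they cannot remove extra random noise in older tissue. It would also go too far to expect women with two core samples to show whether reductions come from sample type. That subset would be selected partly by diagnosis and would be small. For women with atypia or LCIS, even core-to-core pairs change position by design under Appendix F: lateral or above at baseline, medial or below afterwards.

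**What to change.** Before unblinding, amend Section 11.0 as follows.

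1. Add baseline source (diagnostic biopsy versus research core) and the three stratification factors as covariates in the primary between-arm model. Source should be identifiable from specimen records: Section 15.0 lists the two kinds of baseline tissue separately, and Section 6.8.3 has specimen information entered in RAVE.
2. Record the planned post-treatment route (core or surgical) before treatment starts, and add it as a covariate only for that reason. It is not among the recorded items in Section 9.3.2, and using the route actually taken would condition on something settled after randomisation.
3. As a supportive sensitivity analysis, report within-arm changes, placebo included, for women with a fresh research-core baseline and a core post-treatment sample.
4. State that within-arm changes will be interpreted against the placebo arm.

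The source terms cost one to two degrees of freedom. The stratification factors cost (3 − 1) + (3 − 1) + (2 − 1) = 5 more, out of 70 in the two active arms. There is no gain if source has no effect, and the subset in item 3 will be small and will differ by diagnosis. No visits, tissue or participants are added.
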